**8.3 If identifiers will be obtained, indicate how the identifiers will be stored.**

*If you will obtain information on participants' substance use disorder from a treatment provider, then only answer this question for all other data not related to substance use records (e.g., self-report data). All confidentiality and data security questions around substance use records should be recorded in [Appendix J](#).*

Not applicable; identifiers will not be obtained.

Identifiers will be stored separately from study data and a key or code will be kept.

**Describe where the data study, identifiers, and key will be stored, and state the retention period:**

1. Participants will be assigned an identification number which will be affixed to all collected data. Linkage between participant identity and identification numbers will be stored in a password protected electronic file on a secure network drive at Public Health Management Corporation accessible only by key study staff.
2. Participant enrollment spreadsheet containing identifying information will be sent to WTV via encrypted email and in a password protected spreadsheet. This file will not be connected to study data.
3. Electronic obtained consent forms will be stored in a separate restricted folder located on a secure network drive at Public Health Management Corporation accessible only by key study staff.
4. Identifying data (e.g., informed consent forms), screening data, and survey data will be kept for a period of five years after the end of the pilot study as required by NIH/NIDA and then deleted. The information will enable us to ensure pilot study participants do not enroll in a future full research trial.
5. Contact information will be deleted one year after the end of the pilot study.

Identifiers will be removed or destroyed.

**Describe how identifiable data will be de-identified or destroyed. Include information on how, when, and by whom (by role or position, not by name):**

5 years after study completion, all identifying information will be destroyed by PHMC staff.

Identifiers will not be removed or destroyed.

**Provide the rationale for retaining identifiable data and state the retention period. Include information on how and where the identifiable information will be stored:**

## 9 RISKS AND BENEFITS

### 9.1 Select all of the **reasonably foreseeable** risks of harm, discomforts, and hazards to the participants and others as a result of study participation.

**Breach of confidentiality** to records containing identifiable private information or biospecimens

Disclosure of participants' responses outside of the research context could place the subjects at risk of **criminal or civil liability**

Disclosure of the participants' responses outside of the research context could be **damaging** to the participants' financial standing, employability, insurability, education, reputation, social relationships, services, or eligibility services

**Psychological discomfort or distress** from providing or being exposed to personal or sensitive information

Possibility of or perceived **invasion of privacy** to the participant or their family

Possibility of or perceived **coercion or undue influence** to participate in the study (in Aim 2)

Presentation of materials which some participants may consider **sensitive, offensive, or threatening**

**Physical or psychological harm** such as pain, injury, or disease including side effects from drugs and devices

Other (please specify): Disappointment with the randomly assigned training program.

No risks

### 9.2 For each risk selected above, describe the magnitude, probability, duration, and/or reversibility of the harm, discomfort, or hazard.

This study poses minimal risks to participants. Any individuals experiencing significant psychological distress or perceived invasion of privacy from audiotaping are free to refuse to participate or to withdraw from the study. For other participants, if the risks outlined above do occur, we anticipate the magnitude to be low because of the protections we have put in place to protect identity, privacy and confidentiality of participants. The possibility of perceived or undue

influence to participate in the study is likely to be low due to the precautions we have put in place to mitigate this risk. All of these potential harms are transitory or reversible.

### **9.3 For each risk selected above, describe how you will manage or minimize the risk.**

1. **Risk Resulting from a Breach of confidentiality** – Data collected in the study will be kept strictly confidential and will not be shared with anyone outside of the research team. We have developed strict protocols for collecting, securing, storing, and transmitting data. All study staff must complete a Human Subjects training protocol. All research specific materials will be coded with a research number to de-identify the data and will contain no other identifying information to protect participant confidentiality. Participants will be assigned an identification number which will be affixed to all collected data. Linkage between participant identity and identification numbers will be stored in a password protected electronic file. In addition, linkage between participant identity and online user name will be stored in a password protected electronic file. PHMC computer spreadsheets containing data and SPSS data sets will be saved in password protected files on a secure server located at Public Health Management Corporation and accessible only to designated research staff. WTV computer spreadsheets containing data will be saved in a restricted project folder on a secure Google drive. All research instruments will be computerized for this study, and the data will be entered via the Web using Alchemer platform. R&E Group maintains a Business Associate Agreement with Alchemer, allowing staff to securely collect private and confidential information in compliance with the Health Insurance Portability and Accountability Act (HIPAA), Family Educational Rights and Privacy Act (FERPA), and other applicable data security and protection laws.
2. **Risk Resulting from Discomfort or Distress Completing Research Measures and Procedures** – Before giving consent, participants will be informed of potential discomforts from completing research activities.
  - a. **Discomfort associated with being audiotaped during the focus group, individual interviews, or mock or actual sessions.** We will help participants to understand that feeling uncomfortable when being audiotaped is usually transitory. For participants submitting audiotapes of mock or actual client sessions, we will clarify that our goal is to evaluate the training programs, not their abilities per se. If participants experience significant distress such that it makes participation uncomfortable for them, they will be reminded that they can leave the study at any time.
  - b. **Discomfort associated with the training intervention (Aim 2 only)** - The level of distress associated with training interventions is expected to be similar to that which they would experience during any training program and is not a function of the research participation per se. Nonetheless, participants will be informed about this possible risk before consenting and will be told that they can withdraw from the study at any time without penalty. If participants in the TMC condition are experiencing difficulty, discomfort, or distress associated with locating CSOs for actual client sessions, we will help facilitate a client match for them from our We The Village community of family members with a loved one struggling with OUD. If they are experiencing discomfort due to concerns about protecting client confidentiality for those clients participating in videotaped sessions, we will discuss with them steps to ensure client consent and to protect client confidentiality.
3. **Disappointment associated with the training intervention (Aim 2 only)** – It is possible that counselors will be disappointed with the training condition to which they are randomly assigned. Counselors assigned to the T and TM conditions may be disappointed that they did not receive a more intensive training opportunity that would allow them to become certified as CRAFT counselors. Should these individuals wish to pursue CRAFT certification through We The Village after their research participation has ended they will not be charged for the components they have already received and can complete certification at a reduced cost. Counselors who are randomly assigned to the TMC training program may be disappointed that they did not receive a less intensive training program. These individuals, like all study participants, are free to withdraw from the study at any time.
4. **Risk Resulting from Possible or Perceived Invasion of Privacy** - Participants are at risk for harm as a result of being identified as a study participant. Participants will be informed of this risk during the consent process. Participants will receive instruction on how to protect their identity by creating strong passwords, completing training and research activities when they have enough time and privacy to participate, and using unique usernames when participating in online study activities. The likelihood of this occurring is small.

- a. All project staff will be required to undergo training in confidentiality procedures, which reviews data handling procedures as well as addressing questions about participants posed by individuals outside of the immediate project staff and by project staff members who do not need the information requested. Certification of successful completion of this training is kept in the appropriate project binder. Should any breaches of participant confidentiality occur during the course of the study, they will be reported to the relevant IRB and DSMB.

**Aim 2 only:**

- b. Efforts to contact participants for the 12-week post enrollment follow-up assessment will make no mention of the study until it is established that the participant has been reached. Access to participants' contact information will be limited only to research staff members who need to contact a participant for study purposes. Any information on paper documents containing participant identifiers will be kept in a locked filing cabinet separate from the data. Research staff affiliated with this project will destroy all identifying information 5 years after the study has been completed.
- c. Data collected as part of the online training procedures will also be kept confidential. Participants will be instructed to create a username that does not use their last name. Participants can request for their user names to be changed at any time during the study. Participants will be instructed to make sure that they are in a private area before revealing any personal information during an online session or, if applicable, during a video or telephone meeting with a CRAFT trainer. They will also be asked to consider using private telephones (no extension lines) when possible. For those participating via Zoom, Zoom ensures information is not stored in their network; the data is only transmitted during a session. WTV will pay to use a HIPAA protected Zoom account to reduce risks associated with confidentiality and privacy. Participants will receive a secure link to access sessions, so no one other than the intended counselor and staff can attend. Participants who elect to receive text messages or emails will be instructed to use a password to access telephone/email content and to delete messages immediately after responding to them. Audio recorded sessions will be recorded by our trained standardized patient (SP) or participants who have been assigned to receive coaching (Program 3). Both will be trained to upload the audiotape immediately to a secure system, which is no different than if they were to seek certification outside of the study. Once uploaded it will be deleted from the recording device.

5. **Risk Resulting from Perceived Pressure to Participate by Employers** – It is possible that some participants (e.g., counselors) could learn of the focus groups or the training pilot study from their employers and feel pressure to participate or to answer questions or give feedback in a particular way. To protect against this risk:

- a. All employers who are approached to assist with recruitment will be informed of the necessity that research participation is voluntary. They will be told that they cannot require counselors to participate and cannot administer consequences to counselors who do not participate. They will be told that counselors must meet eligibility criteria to participate, so the fact that a counselor does not participate does not mean that they refused to do so. Should an employer inquire about the reasons a counselor did not participate, they will be told the person was not eligible (voluntary participation is an eligibility criterion) and reminded that they should not pressure employees to participate.
- b. All participants will be assured that their participation is voluntary and that we will not provide any information about their participation (i.e. whether they agreed to participate or their responses) to any outside parties. Counselors will not participate in the same focus groups as their supervisors or administrators at their place of employment.

***For protocols that meet the criteria for exempt research, skip to Section 10.***

**9.4 Are there any risks to individuals related to pregnancy, fertility, lactation, or effects on a fetus or neonate? If yes, describe how you will manage or reduce this risk.**

*Some studies will require unique considerations if a participant becomes pregnant during the study (e.g., discontinuation of a diet-based intervention or medications).*

No. We are conducting a behavioral online intervention that poses no risks to participants who are pregnant or who become pregnant during the study.

**9.5 Describe whether participants who become pregnant will be able to continue their participation in the study. If they will continue to be included in the study, describe any measures to accommodate the pregnancy, if applicable.**

Yes. Participants who become pregnant during the study will be able to continue. The proposed study is a behavioral health training intervention and is conducted online. We do not expect pregnant participants to require additional accommodations, because they can participate via a smartphone or computer at any location.

**9.6 Describe the potential direct benefits to individual participants or to others as a result of study participation. Indicate if there may not be any direct benefits to participants or to others.**

**Aim 1 - Qualitative Review:** Some professionals enjoy providing feedback and sharing their experience to improve future programs; however, we anticipate no direct personal benefit to participants beyond this.

**Aim 2 - Training Intervention:** All counselor participants receive training free of charge, which they may perceive as a benefit. It is possible that the training will increase their effectiveness as counselors or allow them to work with new populations (e.g., CSOs), which they may perceive as benefits. However, we anticipate no direct benefit to counselors beyond this.

**9.7 Define reportable and non-reportable Adverse Events (AEs).**

**Reportable AEs:**

Will be defined as: significant discomfort from answering research questions or participating in the focus group, individual interview, or training intervention such that the participant decides to stop their participation or reports new diagnoses of depression, anxiety, or panic attacks. We will also report coercion or perceived coercion to participate in the study as an AE.

**Non-reportable AEs:**

Clinically insignificant events are not considered AEs. Examples of clinically insignificant events include mild viral illness (e.g., colds, flu, and runny nose), common headaches, minor scratches, and mild symptoms or problems associated with medical conditions or accidents. As per the definition of AEs, only significant worsening of problems or new problems will be reported as AEs. We will monitor attrition rates, but drop out from the study will not be reported as an AE.

**Reportable SAEs:** will be defined as death; a life-threatening event such as suicidal attempt, or inpatient hospitalization (including psychiatric hospitalizations) due to suicidal behavior, or psychiatric distress; or substance use overdose; or an event that extends an existing hospitalization as defined above.

**9.8 Define reportable Serious Adverse Events (SAEs). Choose one or both as applicable to your study.**

Any adverse event that:

1. Results in death;
2. Is life-threatening (places the subject at immediate risk of death from the event as it occurred);
3. Results in inpatient hospitalization or prolongation of existing hospitalization;
4. Results in a persistent or significant disability/incapacity;
5. Results in a congenital anomaly/birth defect; or

6. Based upon appropriate medical judgment, may jeopardize the subject's health and may require medical or surgical intervention to prevent one of the other outcomes listed above.

*(OHRP Guidance on Unanticipated Problems and Adverse Events; January 15, 2007)*

Other, or in addition to the above (*please describe*):

**9.9 Describe plans to identify, monitor, manage, and report AEs and SAEs. Include information on the method and frequency of collecting AE and SAE information (e.g., weekly through telephone calls, monthly at study visits, every time the subject comes to the clinical setting), the individuals responsible for collecting this information (e.g., research assistants, case managers, counselors), and the start and end of collection (e.g., from the participant's first exposure to the intervention to their last study visit).**

All WTV and PHMC staff who interact with participants will be trained on the definitions of reportable and non-reportable AEs and SAEs and the way to complete the forms reporting them. The PI and [name] meet regularly with CRAFT trainers to track and to document any AEs and SAEs. The WTV clinical team will be interacting with participants in the CRAFT interventions on a regular basis and will be responsible for collecting AE and SAE information shared during their interactions and reporting them to the PHMC team. In addition, the Research Coordinator will document information related to AEs and SAEs shared when contacting participants.

All adverse and serious adverse events occurring during the study are documented on a form, reviewed and signed by the PI, [name] or [name], and reported to the IRB. All SAEs are reported to the IRB within 48 hours of our awareness of the event (24 hours for fatal events). A summary of all SAEs and AEs that occurred during six-month pilot study will be included in any progress reports to the IRB. We will begin to collect AE and SAE information between the first intervention session and their 12-week post enrollment assessment.

**9.10 Will you submit or have you submitted the protocol for additional oversight by a Data and Safety Monitoring Board (DSMB)?**

Yes:

- The protocol will be submitted to PHMC's DSMB.
- The protocol will be submitted to an external DSMB.
- An external DSMB or monitoring committee has reviewed the study. All reports are attached.
- No, a DSMB is not needed for this study

Cover Page: Statistical Analysis Plan
We The Village Counselor Training Study
NCT05875142
Document Date: 09.26.23

Statistical Analysis Plan

Our statistical analysis focuses on a primary endpoint as well as a number of secondary endpoints of interest. The data derive from questionnaires collected from participants in the study. The final enrollment involved three groups: T – Digital Tutorial Overview, TM – Digital Tutorial Plus Training Materials, and TMC – Digital Tutorial Plus Training Materials Plus Feedback and Coaching, with 15, 16, and 16 subjects enrolled, respectively.

1. **T – Digital Tutorial Overview:** Participants assigned to T were given access to a digital tutorial consisting of a curriculum dashboard for review of 10 modules, including videos, PDFs, text and quizzes, which are to be self-administered over two weeks. Modules remain available during the 10-week post tutorial period. Participants receive weekly contact encouraging engagement in all of the materials available to them.
2. **TM – Digital Tutorial Plus Training Materials:** Participants receive the digital tutorial (T) as described above plus access to 10 modules of digital training materials released weekly over the 10-week post tutorial period for self-study. Participants receive weekly contact encouraging engagement in all of the materials available to them.
3. **TMC – Digital Tutorial Plus Training Materials Plus Feedback and Coaching:** Participants receive the digital tutorial (T) plus the digital Training materials as described in the two arms above plus they submit audio recordings of sessions with clients and receive feedback on their application of CRAFT and coaching on how to improve. Participants receive weekly contact encouraging engagement in all of the materials available to them.

Our comparisons are all treatment/control comparisons of T with TM, and T with TMC.

1. Primary Hypothesis
 - 1.1. At 12 weeks (after study start), participants assigned to the TMC condition will demonstrate the highest CRAFT procedure fidelity (measured in audiotaped sessions with a standardized patient) followed by TM and then T.
Rationale: Direct observation measuring content of CRAFT delivered in treatment sessions is our primary outcome as this provides the best assessment of counselor adherence and skill and is consistent with previous studies.^{7,10,41} Our hypothesis that TMC will produce greater use of CRAFT than T (or TM) is based on the results from previous trials comparing a workshop only to workshops plus feedback and coaching.^{7,10,41}
2. Secondary Hypotheses
 - 2.1. Participants assigned to the TMC condition will demonstrate the highest CRAFT knowledge followed by TM and then T, in their 12-week knowledge test.
Rationale: Results from previous controlled trials have shown no differences in counselor knowledge pre- to post-workshop, but increases have been seen when fact sheets and supervision are added after the workshop.^{39,57-58}
 - 2.2. Participants in all conditions will perceive increased implementation potential over time (pre-tutorial, post-tutorial, 12 week follow up), but at 12 weeks implementation potential will be lower for TMC compared to TM and T.
Rationale: In a CBT (Cognitive Behavioral Therapy) web-based training study implementation potential of three training programs increased over time, but a condition involving expert supervision was seen as more difficult to implement.³⁹

2.3. Participants assigned to the TMC condition will report that more IPs have entered treatment compared to TM and T at 12-weeks (after study start) follow-up surveys. *Rationale:* This hypothesis is based on the results from previous trials examining counselor fidelity^{7,10,41} and studies showing that CBT fidelity enhances treatment outcome.⁵⁹⁻⁶⁰ *We consider this hypothesis exploratory because the 6 month timeline will not be sufficient to adequately test for differences in treatment entry, as there would not be much time after all counselors completed training for them to complete CRAFT with CSOs.*

Data Analysis

Primary and secondary hypotheses were investigated by computing the improvement from baseline to 12-week timepoints. One-sided independent samples T-tests were used for pairwise comparisons of the three conditions. One-sided tests are appropriate for our hypothesized conditions: the alternative hypotheses for which we seek evidence is TMC is better than T, TM is better than T, and TMC is better than TM.

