## 2.4 List the study inclusion criteria.

**Aim 1 - Qualitative Review:** We will sample individuals from 4 groups (n=3/group) including:

- Members of WTV's Subject Matter Advisory Board (SMAB)
- CRAFT trainers or experts
- Counselors working in addictions, or
- Addiction program leaders (Addiction Administrators)

These individuals must be

1. 19 years or older
2. Able and willing to participate in audio recorded focus groups and individual interviews
3. Demonstrates complete understanding of the requirements for participation in the study by reading and signing the consent form

**Aim 2 - Training Intervention:** We aim to enroll 45 participants, meeting the following criteria.

1. Is over 19
2. Lives in the US
3. Working in a counselor-related profession
4. Has not been trained in CRAFT
5. Could provide at least 45 minute individual counselor sessions to at least one CSO (CSO)
6. Counseling work involves clients affected by OUDs, or might if they learned CRAFT
7. Is able and willing to submit the required session audiotapes and participate in the tutorial and training and intervention activities over the course of the 12-week study
8. Reports having access to a computer and smartphone with internet access, email, and word processing capability
9. Demonstrates complete understanding of the requirements for participation in the study by reading and signing the consent form
10. Provides valid locator information to allow research and CRAFT training staff to contact them to schedule study-related appointments
11. Completes the first assessment mock session with our standardized patient (SP) and pre-tutorial surveys

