### **Aim 2- Training Intervention:**

Study procedures are outlined in the figure below. After screening, eligible participants complete the online informed consent form and the locator form. The locator form records the participant's home and work telephone, address, email, and the contact information of others who may be able to assist research staff to reach the participant, if needed. This information will be used to prompt participants to join the scheduled interview. Only study staff will have access to this information. Participants will be contacted primarily through email to ask them to complete surveys or to schedule online mock counseling sessions, but we will secondarily use text, calls, letters, and social media direct messaging as reminders. Participants will complete the self-administered baseline instruments using Alchemer software and be scheduled to complete an online mock counseling session.

After both the baseline survey and mock counseling session have been completed, participants will be randomized into one of three groups using a blocked randomization procedure. The block randomization procedure is used to control for level of education (high school/GED, bachelors, masters, PhD) and training and experience in Cognitive Behavior Therapy (CBT) and Applied Behavior Analysis (ABA), as CRAFT is a CBT based on ABA principles.

We will use an additive components design consisting of: 1) digital tutorial only (T), 2) digital tutorial plus digital training materials (TM), and 3) digital tutorial and digital training materials plus feedback and coaching (TMC). This design will allow us to assess whether the digital training materials improve counselor outcomes relative to the tutorial only, but will not allow us to assess their contribution, if any, to the full training product (TMC).

Follow-up assessments will be conducted after all three groups have completed the tutorial (at 2 weeks) and again at 12-weeks post baseline. All aspects of the study will be conducted completely virtually.

Table 1. Treatment Conditions

TREATMENT CONDITION	Pre-tutorial Assessment	Tutorial	Post-Tutorial Assessment	Experimental Manipulation	12-week Follow-up
	Week 0	Week 1-2	Week 2		Week 12
Digital Tutorial (T)	A	Digital Tutorial	B	Weekly emails encouraging review of specific modules and continued use of the online tutorial	C

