### **Aim 2- Training Intervention:**

#### ***Data collected directly from participants:***

Surveys for baseline, post tutorial (i.e., 2-weeks post baseline), and 12-weeks post baseline assessments will be self-administered using Alchemer software since participants may be located anywhere across the country. The baseline survey consists of socio-demographic questions, such as gender, age, race/ethnicity; other standardized socio-demographic measures adapted from the GPRA instrument; a CRAFT Knowledge Test; and a Training Expectations Form.

Each assessment point also will include an audiotaped mock client session conducted via web conferencing with a standardized patient portrayed by a professional actor. Using a standardized patient will provide a consistent context for measuring counselors' CRAFT skill level at each time-point. The mock session will present the counselor with an opportunity to roleplay CRAFT procedure: teaching the CSO to invite the IP to enter treatment (the same procedure is required for the follow-up assessments). We chose to assess this procedure because a component analysis study showed it positively impacted treatment entry rates and it requires CRAFT skill accumulation (i.e., it incorporates and builds upon skills trained in communication and positive reinforcement). Audio tapes will be coded using the CRAFT Therapist Coding Manual used by [name] to certify counselors.

At the post-tutorial and 12-week follow-up assessments additional surveys will be added regarding satisfaction with the training program, perceptions of usefulness and usability, implementation potential, and program value. Finally, at the 12-week follow-up only, participants will be asked to report the number of CSOs they have worked with over the past 10 weeks, how many of them they implemented CRAFT with, and how many of those CSOs had a loved one who entered new treatment. The measures, their purposes, related hypotheses, and assessment points are provided in the **Measures Table** below.

Table 3. Measures

Purpose	Hypothesis	Measure	Assessment points 
Counselor Knowledge and Skill	i. TMC>TM>T	CRAFT Therapist coding Manual***	Pre-Tutorial, Post-Tutorial, 12 weeks
	ii TMC>TM>T	CRAFT Knowledge Test**	Pre-Tutorial, Post-Tutorial, 12 weeks
Acceptability and Feasibility	iii	Training Expectations Form x	Pre-Tutorial
	iii	Training Satisfaction Survey x	Post-Tutorial, 12 weeks

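### Testing raw baseline-to-12-week change without adjusting for the baseline score is valid and unbiased, but can lose precision for fidelity and knowledge with 15-16 counselors per arm

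*SAP*

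**What the plan says.** The Data Analysis section of the SAP describes the whole analysis in a few sentences. The outcome is a change: "Primary and secondary hypotheses were investigated by computing the improvement from baseline to 12-week timepoints". The test is unadjusted: "One-sided independent samples T-tests were used for pairwise comparisons of the three conditions". No covariate or regression model is named in either document. The SAP's introduction gives the final enrollment for T, TM and TMC, "with 15, 16, and 16 subjects enrolled, respectively".

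A pre-randomisation score exists for two of the SAP's outcomes:

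- **Fidelity.** Protocol section 4.2 states: "Each assessment point also will include an audiotaped mock client session conducted via web conferencing with a standardized patient".
- **Knowledge.** The same section lists, among the contents of the baseline survey, "a CRAFT Knowledge Test; and a Training Expectations Form".

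Both come before allocation. Protocol section 4.1 says "After both the baseline survey and mock counseling session have been completed, participants will be randomized into one of three groups", and one of the Aim 2 inclusion criteria in section 2.4 reads "Completes the first assessment mock session with our standardized patient (SP) and pre-tutorial surveys". Every randomised counselor should therefore have both Week 0 scores.

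Table 3 of the Protocol lists no Week 0 measure for implementation potential, and treatment entry is collected only at 12 weeks. SAP hypothesis 2.2 does name a pre-tutorial time point for implementation potential, which Table 3 does not support. The point below is therefore limited to fidelity and knowledge.

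**The concern.** A t-test on change assumes that each extra point at Week 0 predicts exactly one extra point at Week 12. When that slope is wrong, noise from the Week 0 score is carried into the comparison. ANCOVA estimates the slope from the data instead. With 15 or 16 counselors per arm, lost precision is hard to recover. The contrasts affected are the primary one (fidelity) and the first secondary one (knowledge).

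**Working it through.** **Inputs from the documents.** 15, 16 and 16 enrolled; change score; one-sided pairwise t-tests; no covariate. The documents state no power, SD, correlation, alpha, effect size or dropout rate, so there is no figure of the plan's own to reproduce.

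**Assumptions.** One-sided 5%; a true difference of 0.8 Week 12 SD; rho = 0.3, 0.5, 0.7; s (Week 0 SD / Week 12 SD) from 1 down to 0.4. Improvement is read as the simple difference, since the SAP gives no formula.

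**Is the SAP's test valid?** Yes. In simulation (40,000 trials, 15 v 16, s = 1) the mean estimate was 0.80 for a true 0.80 and within 0.005 of zero under the null. Type I error was 4.8-5.0% at a nominal 5%.

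**Variances**, with Week 12 SD = 1:

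- Change score: 1 + s² - 2·rho·s = (1 - rho²) + (s - rho)²
- Two-arm ANCOVA: (1 - rho²) × [1 + 1/(N - 4)]. At N = 15 + 16 = 31 the factor is 1 + 1/27 = 1.037.

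*Example, s = 1, rho = 0.5.* Change: 0.75 + 0.25 = 1.00. ANCOVA: 0.75 × 1.037 = 0.78. The ratio is 0.78.

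*Example, s = 0.5, rho = 0.5.* Change: 0.75 + 0 = 0.75. ANCOVA: 0.78. The ratio is 1.04, so the change score is slightly better.

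**Power** from the noncentral t distribution (29 df for change, 28 df for ANCOVA), 15 v 16, complete follow-up. Each triple is rho = 0.3/0.5/0.7:

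| s | Variance ratio, ANCOVA / change | Change-score power | ANCOVA power |
|---|---|---|---|
| 1 | 0.67 / 0.78 / 0.88 | 58 / 70 / 88% | 72 / 79 / 91% |
| 0.75 | 0.85 / 0.96 / 1.03 | 66 / 78 / 92% | 72 / 79 / 91% |
| 0.5 | 0.99 / 1.04 / 0.96 | 72 / 81 / 90% | 72 / 79 / 91% |
| 0.4 | 1.03 / 1.02 / 0.88 | 73 / 80 / 88% | 72 / 79 / 91% |

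At s = 1 the difference detectable with 80% power is 1.08/0.92/0.71 SD for change and 0.89/0.81/0.67 SD for ANCOVA. At s = rho = 0.5 it is 0.79 v 0.81 SD.

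**Break-even.** The change score is at least as precise when |s - rho| ≤ √[(1 - rho²)/27]. That is s = 0.12-0.48 at rho 0.3, 0.33-0.67 at rho 0.5, and 0.56-0.84 at rho 0.7.

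**With 20% loss to follow-up** (my assumption; Protocol section 9.7 says only that attrition is monitored), 12 v 13:

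- s = 1: 50/62/81% for change v 63/71/84% for ANCOVA.
- s = 0.5: 64/72/83% v 63/71/84%.

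**Which form of ANCOVA?** Under Protocol section 4.1, TMC counselors may resubmit tapes until they reach certification, so their Week 12 spread may differ from the other arms. I simulated the 15/16/16 design (40,000 runs, rho = 0.5, s = 1, no T v TM effect) with the TMC residual SD at 0.5, 1 and 2 times the others. Type I error for T v TM:

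| Analysis | ×0.5 | ×1 | ×2 |
|---|---|---|---|
| Change-score t-test | 5.0% | 4.9% | 5.0% |
| Two-arm ANCOVA | 4.8% | 4.8% | 4.9% |
| Three-arm ANCOVA, pooled variance | 7.5% | 4.8% | 1.2% |
| Three-arm ANCOVA, HC3 standard errors | 4.3% | 4.3% | 4.3% |

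A pooled three-arm model would therefore replace a small efficiency problem with a validity problem. The two-arm fit does not.

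**The case against.** The strongest reply is that nothing here is wrong. The SAP's analysis is coherent, the study is a pilot that makes no power claim, and the size of any loss rests on quantities the documents do not give.

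For fidelity, the little evidence available points towards a small loss. One inclusion criterion is "Has not been trained in CRAFT", and Protocol section 4.2 describes the tested procedure as one that builds on other CRAFT skills. Scores clustered at a floor in Week 0 would tend to lower both s and rho. At s = 0.3 and rho = 0.1/0.2/0.3, power is 69.0/71.3/73.7% for change and 69.1/70.3/72.3% for ANCOVA, so the SAP's test is level or about one point ahead. The SAP is also dated after enrollment closed and written in the past tense, which limits what can still be changed.

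All of this stands as a limit on the size of the point. It does not remove it. A floor is plausible but not shown. The Protocol blocks randomisation on education and on CBT and ABA training, which suggests that starting ability is expected to vary. A floor in fidelity would not settle the matter for the knowledge test, which is a separate instrument. Even at s = 0.3, a correlation of 0.7 gives 84% for change v 91% for ANCOVA. The pay-off is lopsided: over the values examined, ANCOVA gives up at most about 2 points and gains up to about 15.

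**Conclusion.** The concern holds as an efficiency point. The change-score t-test is valid and unbiased under randomisation, provided 12-week data are not missing differently by arm. It can be clearly less precise than the collected data allow. With equal SDs the assumed power gap is about 15 points at rho 0.3, 9 at rho 0.5 and 3 at rho 0.7. With a Week 0 SD half the Week 12 SD, switching to ANCOVA changes power by -1.3 to +0.9 points. These figures rest on an assumed effect of 0.8 SD, one-sided 5% and the stated values of s and rho. The documents do not show which case applies. Baseline adjustment is worth specifying because it is nearly free whichever case is true.

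**What to change.** For fidelity and knowledge:

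1. Estimate each arm contrast by a two-arm ANCOVA of the Week 12 score on arm and Week 0 score, and report it with its confidence interval.
2. Use a single three-arm model only with HC3 standard errors.
3. Report the Week 0 and Week 12 SDs and their correlation, so that readers can see which case applied.
4. Keep the randomisation blocking factors for a sensitivity analysis.
5. If outcomes had already been analysed when this is changed, leave the t-tests as the stated analysis and present the ANCOVA as a labelled additional analysis.

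**Cost.** No new data. The two-arm fit of 31 counselors spends one degree of freedom, about 4% of variance. Where s is close to rho, power falls slightly: 1.3 points at s = rho = 0.5 with full follow-up, and about 2 points with 20% loss. HC3 is slightly conservative (level about 4.3-4.5%) and costs about one further point of power. If TM's residual SD is half or double T's, the two-arm ANCOVA runs at 5.7% or 4.9%, close to the t-test's 5.5% or 4.8%.
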